3.6. Description of Baseline Data

Demographic details (e.g., age, sex, race, ethnicity, marital status, military service), medical history (e.g., co-morbidities, smoking history), and baseline labs will be evaluated overall, by intervention group, by country (Australia or USA), and by enrollment site.

3.7. Description of Procedure Related Data

Angiographic procedure related details (e.g., type of procedure, inpatient/outpatient status, type and volume of dye administered), study interventions received prior to and during procedure, and information on additional therapy, if any, required during the procedure will be evaluated overall and by intervention group.

3.8. Description of Follow-up Assessment Data

Details on additional angiography procedure, therapies other than angiography, if any, clinical events such as hospital re-admissions, initiation of dialysis, and death within 90 days post index procedure will be evaluated overall and by intervention group.

3.9. Safety Data

The safety information to be collected for this study include the description of the event, distinction between serious and non-serious adverse event, severity and expectedness of the event, relatedness to the study intervention, and outcome of the event. In addition, data on all events will be classified using the Medical Dictionary for Regulatory Activities (MedDRA) (Version 9.0) coding dictionary.

Safety data will be collected for all consented subjects from the date the consent was signed up to 35 days post index angiography procedure for non-serious adverse events, and up to 90 days post index angiography procedure for serious adverse events. If the subject terminates from the study prior to 90 days post index procedure, collection of safety data will cease on termination date.

For reporting to the DMC and inclusion in the final report safety data will be aggregated for the ITT sample only as described in **3.3**. Data will be summarized as follows.

- Frequency and percentages of all non-serious and serious adverse events overall and by intervention group
- Frequency and percentages of all unique subjects with non-serious and serious adverse events overall and by intervention group
- Rates of non-serious and serious adverse events overall, by intervention group, and by center, calculated as # events/ person-time in years

- Tabulation of event type, MEDRA classification, severity, expectedness, relatedness and outcome of all events overall and by intervention group
- Overall hospitalization, dialysis, and mortality rate at 90 days and 1 year overall and by intervention group

4. Sample Size and Power

With a total sample of 7680 subjects equally allocated to each of 4 treatment arms, CSP 587 is powered to detect at least a 25% reduction in the 90-day incidence of MAKE-D for each intervention. Expected event rates used in sample size estimation to achieve 90% statistical power for hypothesis testing are given in Table 4 below. Justification for selecting these rates to estimate sample size and power are provided in the protocol.

Table 4. Expected 90-day Incidence of MAKE-D Endpoint

	Bicarbonate	Saline		
NAC	5.59%	7.46%	6.52%	Overall event rate 7.6%
Placebo	7.46%	9.95%	8.70%	
	6.52%	8.70%		

These estimations assume no interaction between the two active interventions, are adjusted for an O'Brien-Fleming stopping rule with one interim and one final test of hypothesis, and allow for an overall two-sided type I error of 2.5% for each hypothesis being tested. Hence, each of the interim hypothesis for main effect will be tested at p=0.001 level (allowing for 0.1% Type I error), and each of the final hypothesis for main effect will be tested at p=0.024 level (allowing for 2.4% Type I error).

If an attenuation of effect is present due to interaction between Sodium Bicarbonate and NAC, adjustment to the statistical power for 10% to 50% attenuation are given as follows.

Table 5. Statistical Power in the Presence of Effect Attenuation.

% attenuation from interaction between Bicarbonate & NAC	Rate in Bicarbonate/NAC	Rate in treatment (T) group	Rate in control (C) group	% reduction (C-T)/C	Power
No interaction	5.60 %	6.52%	8.7%	25%	90%
10% attenuation	5.78%	6.62%	8.7%	23.9%	87.5%
20% attenuation	5.97%	6.71%	8.7%	22.9%	84%

30% attenuation	6.15%	6.81%	8.7%	21.7%	79.3%
50% attenuation	6.53%	6.99%	8.7%	19.7%	69.4%

Sample recruitment and subsequent event rates will be summarized and presented to the DMC bi-annually as outlined in section 7 below. These reports will be used for monitoring the progress of the study and any modification to the recruitment schedule or the statistical analysis plan will be at the recommendation of the DMC.

5. Statistical Methods

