A total of 7680 subjects recruited from the 33 Veterans Health Administration (VHA) centers are expected to be randomized equally to each of the 4 groups as shown in Table 1 below. An additional 1000 subjects are expected to be enrolled in the 12 non-VHA sites in Australia to augment the data collected in the US.

Table 1. Intervention Groups

	Bicarb	Saline
NAC	Group1: NAC+Bicarb	Group2: NAC+Saline
Placebo	Group3:Placebo+Bicarb	Group4:Placebo+Saline

Compare
NAC vs. Placebo
(Groups 1+2 vs. 3+4)

Compare Bicarb vs. Saline
(Groups 1+3 vs. 2+4)

The primary objective:

As the primary objective, the trial will test two hypotheses:

- (#1) IV isotonic bicarbonate is more effective than saline, and
- (#2) NAC is more effective than placebo

in prevention of major adverse kidney events (need for acute dialysis or 50% increase in serum creatinine at 90 days after angiography) and death (MAKE-D) following coronary and non-coronary angiography. This will be accomplished by comparing the incidence of MAKE-D in groups 1 and 3 combined to groups 2 and 4 combined for hypothesis (#1), and by comparing groups 1 and 2 combined to groups 3 and 4 combined for hypothesis (#2). See **3.5.1**.

Secondary Objective:

The trial will also evaluate the effectiveness of the study interventions for the prevention of 5 individual secondary endpoints (section **3.5.2**) by comparing the treatment groups as in the primary objective. The secondary endpoints are:

- 1)contrast induced acute kidney injury (CIAKI) at day5 after angiography
- 2)death
- 3)major adverse kidney endpoints (MAKE)
- 4)hospitalization with acute coronary syndrome, heart failure, or cerebrovascular accident
- 5)all-cause hospitalization.

Tertiary Objective:

The trial will explore the effectiveness of the study interventions for the prevention of the following outcomes (see **3.5.3**), within one year following coronary or non-coronary angiography by comparing the treatment groups as in the primary objective. The tertiary endpoints are:

- 1) development of end stage renal disease (ESRD), and
- 2) death.

3. Investigational Plan

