5.1. Handling of Missing Data in Analysis

Up to 3% of subjects have been estimated to drop out prior to end of follow-up before 90 days. Distribution of subjects lost to follow-up and missing data on key variables across the treatment groups will be monitored throughout the study.

Missing endpoint data will not be imputed. All those with missing endpoint data either due to attrition or active withdrawal of consent will be excluded from primary analysis. Those who completed 90 days of follow-up and have initial 90 day blood-draw demonstrating a $\geq 50\%$ increase in serum creatinine but are missing the confirmatory blood draw will not be included in the primary analysis as having met the primary endpoint, however, they will be included in the sensitivity analysis as having met this endpoint data. See section 5.3.5.

5.2. Univariate and Bivariate Distributions of Baseline, Procedure Related, Safety and Follow-up data

- In general, the number of observations, mean, median, standard deviation, minimum, and maximum will be calculated for continuous variables. The number of decimal places will be to plus two decimal places.
- Frequencies and percentages will be calculated for categorical data.
- Distribution of continuous variables and proportions of categorical variables will be tabulated by intervention group, and t-test and chi-square tests will be performed to evaluate if these variables are balanced across 4 intervention groups.
- Baseline is defined as the randomization visit.

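### SAP 3.9 tabulates adverse events and SAEs by the four treatment cells and specifies no bicarbonate v saline or NAC v placebo comparison of them

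*SAP*

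**What the plan says.** SAP 3.9 governs safety summaries for both the DMC and the final report. It asks for "Frequency and percentages of all unique subjects with non-serious and serious adverse events overall and by intervention group". Event counts, event rates per person-year (also by center) and the MedDRA tabulations carry the same breakdown, as does the last item: "Overall hospitalization, dialysis, and mortality rate at 90 days and 1 year overall and by intervention group".

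Section 3.9 does not define intervention group. Two other places indicate the meaning:

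- The table in SAP section 2 headed "Table 1. Intervention Groups" lists Groups 1 to 4, one per treatment combination.
- SAP 5.2, whose heading includes safety data, says "t-test and chi-square tests will be performed to evaluate if these variables are balanced across 4 intervention groups".

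The margins are written out beside that same table for efficacy: fluid as "Groups 1+3 vs. 2+4" and NAC as "Groups 1+2 vs. 3+4". The secondary and tertiary endpoints are also assessed "by comparing the treatment groups as in the primary objective". The interim analysis in SAP 5.6 uses the margins for MAKE-D.

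Protocol section XII.B lists side effects separately for sodium chloride, sodium bicarbonate and NAC.

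**The concern.** The safety questions here are mostly about one factor at a time. Metabolic alkalosis is listed for bicarbonate, metabolic acidosis for saline, and diarrhea, nausea and vomiting for NAC. In a 2 x 2 factorial trial that assumes no interaction, the natural contrast for such an event is the margin, which uses every patient. The plan takes that contrast for efficacy but does not state it for adverse events and SAEs.

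If the DMC and final tables show only four columns, a reader who wants to know whether bicarbonate raises the rate of some event has two choices: compare single cells by eye, or rely on an overall four-group test. The first uses half the patients. The second uses all of them but spreads a one-factor signal over 3 degrees of freedom and yields no risk difference for either agent. Both lower the chance of recognizing a real excess. The DMC can recommend stopping for safety (protocol XVI.B), so this bears on trial conduct as well as on the final report.

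**Working it through.** **Inputs.** From the documents: 7,680 patients, 1,920 per cell, 1:1:1:1 allocation (protocol V and VII.B), so 3,840 per margin. For efficacy: 8.70% v 6.52%, two-sided 0.025 per factor, 90% power, 7,450 patients before and 7,680 after 3% loss (protocol XVII.F). The documents give no adverse event rates by arm. I assume control risks of 1% to 10%, relative risks of 1.25 or 1.5, two-sided 5%, and no interaction.

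**Step 1: the plan's own figure is a marginal one.** Per margin,

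n = [z(α/2)·√(2p̄(1−p̄)) + z(β)·√(p₁(1−p₁) + p₂(1−p₂))]² / (p₁−p₂)²

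With p₁ = 0.087, p₂ = 0.0652, z(α/2) = 2.241 and z(β) = 1.282, n is about 3,671, a total of 7,342, or 7,570 after dividing by 0.97. At the final-look alpha of 0.024 the totals are 7,406 and 7,636. All are within 3% of the stated 7,450 and 7,680. The trial is therefore sized on 3,840 v 3,840.

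**Step 2: precision.** A cell-against-cell contrast has 1,920 v 1,920, so its standard error is √(3,840/1,920) = 1.41 times that of the margin. With both arms near 2%, the 95% half-width is 1.96·√(2 × 0.02 × 0.98/n): 0.89 percentage points for n = 1,920 and 0.63 for n = 3,840.

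**Step 3: power at 2% v 3%.** Power = Φ[(|p₁−p₂| − 1.96·SE₀)/SE₁], where SE₀ uses the pooled and SE₁ the separate variances.

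- Margin, n = 3,840: SE₀ = 0.003563, SE₁ = 0.003561. (0.01 − 0.006984)/0.003561 = 0.847, so power is 80.2%.
- Cell against cell, n = 1,920: SE₀ = 0.005039, SE₁ = 0.005036. (0.01 − 0.009876)/0.005036 = 0.025, so power is 51.0%.
- Four-group chi-square, 3 df: two cells at 2%, two at 3%, mean 2.5%. Noncentrality = 4 × 1,920 × 0.005²/(0.025 × 0.975) = 7.88. Against the 5% critical value of 7.81, power is 64.7%.

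**Step 4: other assumed risks.**

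| Control v treated | Margin | Four-group, 3 df | Cell v cell |
|---|---|---|---|
| 1% v 1.5% | 50.5% | 34.9% | 28.6% |
| 2% v 3% | 80.2% | 64.7% | 51.0% |
| 5% v 6.25% | 66.2% | 49.2% | 39.0% |
| 10% v 12.5% | 93.4% | 84.1% | 68.9% |

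The margin has the highest power in each row. The additional 1,000 non-VA patients would change the counts but not the ratio of one half.

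**The case against.** Several points on the other side stand.

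- **No cell-against-cell harm test is planned.** A reader might infer that every harm comparison uses half the patients. SAP 3.9 lists frequencies, percentages and rates, and names no pairwise test. The only stated test covering safety data is the four-group one in SAP 5.2, which uses all patients. The 51% therefore describes what a reader of the columns might do, and the fairer contrast with the plan is 65% against 80%.
- **Some harms are already compared at the margins.** A reader might infer that safety is examined only by cell. Death, MAKE, cardiovascular hospitalization (including heart failure) and all-cause hospitalization are secondary endpoints with bicarbonate v saline and NAC v placebo odds ratios (SAP 5.4). One-year death and ESRD follow the same strategy (SAP 5.5).
- **No information is lost.** The cells are disjoint, so subjects, events and person-time can be summed to either margin. The protocol also gives the DMC statistical support for judging differences.
- **The shell tables are held elsewhere.** The SAP gives only their titles, so they may already show margins. Reading intervention group as four cells is likely but inferred.
- **Four cells have a use.** Data on interaction are limited, as protocol VIII.C.5 admits, and combination-specific harm shows only in the cells.

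These points narrow the concern without removing it. The four-group test is framed as a balance check, gives no direction, and does not attribute a signal to fluid or NAC. The ability to sum cells is not an instruction to do so, and no effect measure or interval is specified. The provision for statistical support sets no level of comparison.

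**Conclusion.** The point holds as a gap in prespecification. For adverse events and SAEs outside the efficacy endpoints, the SAP states four-cell tables and no comparison by factor. At an assumed 2% v 3%, moving from the stated four-group test to the margin raises power from about 65% to about 80%. Across the assumed risks in the table the gain is roughly 9 to 17 percentage points.

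These figures rest on assumed event rates, two-sided 5%, no interaction between fluid and NAC, and full cells of 1,920. They also rest on reading intervention group in SAP 3.9 as the four cells. The documents do not support the stronger conclusions that patients are discarded, that all safety outcomes lack a marginal comparison, or that the DMC could not obtain one. Nothing here threatens the validity of the trial. It is a free improvement.

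**What to change.** In SAP 3.9, add for adverse events and SAEs a bicarbonate v saline contrast (Groups 1+3 against 2+4) and a NAC v placebo contrast (Groups 1+2 against 3+4). Give each a risk difference in subjects with an event and its confidence interval. Make the same addition to DMC tables D1 to D5 if the shells do not already contain it. Keep the four-cell columns as supporting detail for combination-specific harm, and define intervention group in 3.9 so that its meaning need not be inferred.

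The cost is extra columns in existing tables, from data already collected. Sample size, visits and the efficacy analysis are unaffected.

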**Table 10 - Sample size for selected response rates**

| Rate in control (C) group | Rate in treatment (T) group | % reduction (C -T)/C | Total sample size 80% power b | Total sample size 90% power b |
|---------------------------|-----------------------------|----------------------|--|--|
| 7.0                       | 4.90                        | 30%                  | 5,030                                    | 6,562                                    |
| 7.0                       | 5.25                        | 25%                  | 7,432                                    | 9,688                                    |
| 7.0                       | 5.6                         | 20%                  | 11,924                                   | 15,546                                   |
| 8.7                       | 6.1                         | 30%                  | 3,995                                    | 5,196                                    |
| 8.7 a          | 6.52 a           | 25% a     | 5,900 a                       | 7,680 a                       |
| 8.7                       | 7.0                         | 20%                  | 9,440                                    | 12,317                                   |
| 10.4                      | 7.3                         | 30%                  | 3,271                                    | 4,285                                    |
| 10.4                      | 7.8                         | 25%                  | 4,844                                    | 6,314                                    |
| 10.4                      | 8.3                         | 20%                  | 7,763                                    | 10,123                                   |

a rates and sample size for proposed model (with adjustment for losses to follow-up)

b adjusted for an O'Brien-Fleming stopping rule with one interim and one final test of hypothesis and considering a two-sided type I error = 0.025.

Thus, based on a 90 day event rate of 8.70% in the control group (i.e., saline or placebo) and

[name], [name]: CSP#578 “Prevention of Serious Adverse Events Following Angiography”  

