### **G. Interim analysis**

Using the O’Brien-Fleming procedure, we will carry out an interim analysis after half the expected number of events (292 events) has occurred, roughly after 18 months, to determine if either intervention shows a substantial beneficial effect. We will compare the proportion of subjects with a MAKE-D event with and without the use of bicarbonate and will compare the proportion of subjects with a MAKE-D event with and without the use of NAC. The respective absolute differences are dBicarbonate and dNAC. At the interim analysis, a z-value of 3.18 will be needed to reject the null hypothesis with Type I error of 2.5%. At the final analysis a z-value of 2.25 will be needed to reject the null hypothesis with Type I error of 2.5%.

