5.6. Interim Analysis

This study is expected to enroll 7680 subjects over a 2.5 years (or 30 month) recruitment period. At 18 months, i.e., after 15 months of recruitment plus 3 months of follow-up, approximately half or 3840 subjects are expected to be enrolled with primary endpoint events occurring in roughly 292 subjects (7.6%). Using the O'Brien-Fleming procedure, we will carry out an interim analysis to determine if either intervention shows a substantial beneficial effect.

We will compare the proportion of subjects with a MAKE-D event among those with and without the use of bicarbonate and among those with and without the use of NAC.

We will follow the same analytic strategy as described in **5.3** for primary analysis, where the odds of having an outcome will be estimated by modeling the outcome as a binary indicator of presence or absence of the MAKE-D event.

We will derive the Odds Ratios (i.e., the odds of the event of interest at 90 days post angioplasty among those allocated to IV isotonic sodium bicarbonate therapy compared to those allocated to IV isotonic saline, and among those allocated to NAC compared to those allocated to Placebo), and test for statistical significance of these odds ratios at $p=0.001$ level, assuming no interaction between the active interventions.

If the Wald Chi-square test has $p \leq 0.001$ for regression coefficient β_1 in Model 2, then the null hypothesis of $H_0: \beta_1 = 0$ will be rejected and alternative hypothesis of $H_a: \beta_1 \neq 0$ accepted. If the 95% Confidence Interval of the Odds Ratio does not include 1 and $\beta_1 < 0$, we can conclude that Bicarb is superior to Saline. Conversely, if the 95% Confidence Interval of the Odds Ratio does not include 1 and $\beta_1 > 0$, we can conclude that Bicarb is not superior to Saline.

Similarly, if the Wald Chi-square $p \leq 0.001$ for regression coefficient β_2 in Model 2, then the null hypothesis of $H_0: \beta_2 = 0$ will be rejected and alternative hypothesis $H_a: \beta_2 \neq 0$ accepted. If the 95% Confidence Interval of the Odds Ratio does not include 1 and $\beta_2 < 0$, we can conclude that NAC is superior to Placebo. Conversely, if 95% Confidence Interval of the

Odds Ratio does not include 1 and $\beta_2 > 0$, we can conclude that NAC is not superior to Saline.

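### The SAP's operative levels (p = 0.001 and 0.024) do not match the protocol's O'Brien-Fleming boundaries (z = 3.18 and 2.25): a minor, conservative mismatch that matters only at the interim

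*SAP*

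**What the plan says.** The two documents agree on the design. The SAP's calculations assume an O'Brien-Fleming "stopping rule with one interim and one final test of hypothesis". As for the error rate, SAP section 4 says that they "allow for an overall two-sided type I error of 2.5% for each hypothesis being tested". The protocol's footnote to Table 10 makes the same adjustment, "considering a two-sided type I error = 0.025". Protocol XVII.G places the interim "after half the expected number of events (292 events) has occurred", and SAP 5.6 expects the same 292 events among 3,840 enrolled subjects.

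They differ on the thresholds:

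- Protocol XVII.G, for the first look: "At the interim analysis, a z-value of 3.18 will be needed to reject the null hypothesis with Type I error of 2.5" per cent. For the last look, the same section sets z = 2.25 at the same error rate.
- SAP section 4, as a consequence of the O'Brien-Fleming rule: "each of the interim hypothesis for main effect will be tested at p=0.001 level", with 0.024 for the final test. It describes these as 0.1% and 2.4% of Type I error.

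The SAP levels are operative. Section 5.6 rejects at the interim if the Wald p-value is at most 0.001, and section 5.3.2 rejects at the end if it is at most 0.024. The SAP never states z = 3.18 or z = 2.25. Section 5.3.3 gives an overall level of 0.048 for the analyses that follow a significant interaction; this is twice 0.024.

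**The concern.** These thresholds decide whether an efficacy boundary has been met and whether a primary claim is made. If the same data can meet the boundary in one document and miss it in the other, the Data Monitoring Committee has two answers to one question, and the dispute would arise only once the result was known. The SAP also presents its two levels as pieces of Type I error that add to 2.5%. Nominal levels at two correlated looks do not add to the overall error, so that description is inexact however the figures arose.

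**Working it through.** **Inputs.** Two-sided alpha 0.025 per main effect (SAP 4; Protocol Table 10, note b). Two looks, with the interim at half the events, so the information fraction is 0.5 and the correlation between Z1 and Z2 is √0.5 = 0.707 (Protocol XVII.G; SAP 5.6). Event rates 8.70% and 6.52%, and 7,450 patients before loss to follow-up (Protocol XVII.F).

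**1. Reproduce the protocol's boundaries.** For two equally spaced looks, solve for C in P(|Z1| ≥ C√2 or |Z2| ≥ C) = 0.025. This gives C = 2.2505, so the interim z is 2.2505 × 1.4142 = 3.183 and the final z is 2.250. The protocol's figures are correct.

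**2. Put both rules on both scales.**

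| | Interim z | Interim p | Final z | Final p | Overall two-sided error |
|---|---|---|---|---|---|
| Protocol | 3.18 | 0.00147 | 2.25 | 0.0244 | 0.0250 |
| SAP | 3.291 | 0.00100 | 2.257 | 0.0240 | 0.0244 |

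The SAP's interim level is 0.00100 / 0.00147 = 0.68 of the protocol's, about one-third lower. To three decimals, 0.00147 becomes 0.001 and 0.0244 becomes 0.024, which is the SAP pair.

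**3. Check the additive description.** The SAP's levels sum to 0.001 + 0.024 = 0.025, but the rule delivers 0.0244. The protocol's levels sum to 0.00147 + 0.0244 = 0.0259, but that rule delivers 0.0250. In neither case is the sum the overall error.

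**4. What the gap means in events.** Take 292 events in 3,840 subjects, split 1,920 and 1,920, and use the Wald test of the log odds ratio. For 119 v 173:

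- log OR = ln[(119 × 1,747) / (173 × 1,801)] = −0.4046
- SE = √(1/119 + 1/173 + 1/1,801 + 1/1,747) = 0.1237
- |z| = 3.270, p = 0.00108

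| Events | Wald z | p | Protocol (z ≥ 3.18) | SAP (p ≤ 0.001) |
|---|---|---|---|---|
| 118 v 174 | 3.390 | 0.00070 | met | met |
| 119 v 173 | 3.270 | 0.00108 | met | not met |
| 120 v 172 | 3.150 | 0.00163 | not met | not met |

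Exactly one split in each direction separates the two rules.

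**5. How likely the gap is.** Under the design effect with 7,450 patients, the pooled rate is 7.61% and the expected final z is 0.0218 / √(0.0761 × 0.9239 × 2 / 3,725) = 3.548. The expected interim z is 3.548 × 0.707 = 2.509.

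- Crossing at the interim: 1 − Φ(3.18 − 2.509) = 25.1% under the protocol; 1 − Φ(3.291 − 2.509) = 21.7% under the SAP. The difference is 3.4 points.
- Under the null, the chance of an interim z in the gap is 0.00147 − 0.00100, about 0.05%.
- The chance of a final z between 2.250 and 2.257 is about 0.12% under the design effect and 0.045% under the null.
- Overall power is 90.3% under the protocol's pair and 90.2% under the SAP's.

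**The case against.** The strongest reply is that this is rounding. The SAP names the O'Brien-Fleming rule and gives its levels as following from it, and those levels are what the protocol's boundaries become at three decimals. Every difference is in the strict direction, so the 2.5% ceiling holds, and the power cost is about 0.1 point. One event split per direction is affected at the interim, and a trial that misses the SAP's level there simply goes on to a final test.

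Most of this stands. It rules out several stronger readings that a reader might infer:

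- *That the SAP uses a different method, dividing alpha by subtraction and ignoring the correlation between looks.* The SAP describes no such derivation. That the levels add to 2.5% does not show how they were obtained, and rounding explains them at least as well.
- *That Type I error is compromised.* The SAP's rule gives 0.0244, inside the stated 0.025.
- *That the final analysis is at real risk of conflicting verdicts.* The gap there is 0.007 on the z scale.
- *That the documents would force opposite stopping decisions.* Protocol XVII.G gives the z needed to reject the null hypothesis. Protocol XVI makes stopping a recommendation of the Data Monitoring Committee to the program director, not an automatic result of crossing.

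What the reply does not remove is that section 5.6 applies p ≤ 0.001 as written. A rounded threshold used literally is a different threshold, and at the interim the rounding takes off a third of the level.

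**Conclusion.** The point holds as a minor inconsistency in a decision rule. The protocol's boundaries are the correct O'Brien-Fleming values for the design that both documents describe. The SAP's operative levels are slightly stricter, and only the interim difference has any practical size: z = 3.29 instead of 3.18, one discordant split at the planned look, and a 3.4-point lower chance of crossing if the design effect is true. Validity is not threatened.

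The figures assume an interim at exactly half the information, equal arms for each main effect, and the protocol's event rates. With 7,680 analysed instead of 7,450, the interim crossing chances are 26.3% and 22.9%, so the conclusion does not depend on that choice.

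**What to change.** In SAP sections 4, 5.3.2 and 5.6, give the boundaries as |z| ≥ 3.18 at the interim and |z| ≥ 2.25 at the final analysis, with p about 0.00147 and 0.0244 in parentheses. Let the z-values govern: p = 0.0015 corresponds to z = 3.175, so quoting that level alone would leave a smaller gap on the lenient side.

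In section 4, delete the description of the levels as 0.1% and 2.4% of Type I error, and say only that the pair of boundaries gives 2.5% two-sided overall for each hypothesis. In section 5.3.3, align the overall level with the final boundary; if it is meant as twice the final level, 0.048 becomes 2 × 0.0244 = 0.0488.

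The cost is SAP wording. The protocol, sample size, data collection and timing of the interim are unchanged. The edit should be made without sight of comparative results.
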